## Experimental Design Schema

Note: There is a lead in portion using only 420 mg oral daily and 560 mg daily.

## Protocol Synopsis

Protocol Title:
A multi-center phase II study of ibrutinib plus brentuximab vedotin in relapsed/refractory Hodgkin Lymphoma.
Brief Protocol Title (Lay Public):
A phase II study of ibrutinib plus brentuximab vedotin in high-risk Hodgkin Lymphoma
Study Phase:
Phase II with safety lead-in
Participating Sites:

 
▪ City of Hope
 
▪ Cornell
 
▪ UCSD
 
▪ OSU
 

Study Rationale:

Brentuximab vedotin (BV) is an antibody drug conjugate (ADC) consisting of the chimeric antibody SGN-30 (cAC10) chemically conjugated to the anti-tubulin agent monomethyl auristatin E (MMAE). BV binds to CD30 on the cell surface of Hodgkin-Reed-Sternberg cells and is internalized. Upon trafficking to lysosomes, MMAE is released from the conjugate and disrupts the microtubule network. We previously participated in the multi-center phase II pivotal study investigating the use of single agent brentuximab vedotin (BV) in patients with relapsed/refractory Hodgkin lymphoma (HL) post autologous hematopoietic stem cell transplantation (AHCT). This trial showed that BV has an overall response rate of 75%, with a 34% complete response rate and tolerable toxicity. Because of the high response rate, BV was granted accelerated FDA approval for the treatment of relapsed/refractory HL following failed AHCT. Although this drug has high response rates in HL, the complete response rate and the duration of response can be improved.
 
Ibrutinib is a Bruton's tyrosine kinase (BTK) inhibitor, which inhibits activation of the B cell receptor signaling cascade. It has demonstrated activity in patients with relapsed/refractory B cell lymphomas and has already received FDA approval for the treatment of CLL and MCL. Ibrutinib is also an ITK inhibitor, which can be active against activated T cells. It is possible that ibrutinib can inhibit B cells and T cells in the microenvironment of HL. We performed a synergy assay testing the combination of ibrutinib and brentuximab vedotin (the latter previously known as SGN-35) in L428 (HL cell line) and found a synergistic effect. Since there is evidence of synergy in preclinical studies and the toxicity profiles do not appear to be the similar, it is reasonable to combine the two agents in relapsed/refractory Hodgkin lymphoma.

Objectives:

In patients with relapsed/refractory Hodgkin Lymphoma:
 
Primary:
 
 
▪ Evaluate the anti-tumor activity of the two agent combination ibrutinib and brentuximab vedotin, as assessed by complete response (CR) rate.
 
 
Secondary:
 
 
▪ Assess the safety and tolerability of the two agent combination through evaluation of toxicities, including type, frequency, severity, attribution, time course and duration.
 

- Obtain estimates of overall response rate (ORR), response duration and survival (overall and progression-free).
- Describe outcomes of patients who ultimately undergo autologous or allogeneic hematopoietic cell transplantation following treatment with ibrutinib/brentuximab vedotin.

**Exploratory:**

- Collect DNA/RNA from lymphoma specimens and serial plasma samples for future biomarker evaluation.

**Study Design:**

This study will be conducted as a multi-center phase II trial; a Simon Two-Stage (Minimax) Design will be employed. Prior to formally initiating the phase II trial, a *patient safety lead-in* segment will be conducted to ensure there are no unexpected toxicities during cycle 1. Ultimately a total of 39 patients will be treated and evaluated for response at the ibrutinib/brentuximab vedotin doses considered safe -as determined during the *safety lead-in* segment of this study.

The first nine to twelve patients enrolled will be part of the *patient safety lead-in*. Initially, a group of up to 3 patients can be enrolled. Because both brentuximab vedotin and ibrutinib have been extensively studied as single agents with tolerable toxicity profiles, it is assumed that the standard FDA-approved dosing would be tolerable (dose level 2: Ibrutinib 560mg/brentuximab vedotin 1.8mg/kg). However, during the safety lead in patients will initially be treated with 420 mg of Ibrutinib (dose level 1).

Following the *safety lead-in*, the phase II trial will formally be initiated. In the first stage, 19 patients will be entered on the study. If  $\leq 6$  complete responses are seen, the study will be terminated. If at least 7 patients achieve a complete response, the trial will continue to the second stage. At stage 2, 20 additional patients will be entered. At the end of stage 2, if 17 or more patients experience a complete response, the combination will be considered worthy of further study. If  $\leq 16$  patients experience a complete response then no further investigation of the combination is warranted.

In addition to response assessment, using the Cheson Criteria (Cheson et al. 2014), survival, toxicity information, and lymphoma specimens/plasma samples will be collected for exploratory biomarker evaluation.

**Endpoints:**

The primary study endpoint is complete response (CR) rate and is based on the Cheson Criteria (Cheson et al. 2014).

The primary endpoint for the patient *saftey lead-in* segment of the study is toxicity. Toxicity will be scored using the NCI CTCAE v4.0 Scale. Unacceptable toxicity in a given patient is defined as any non-hematologic grade 3|4 toxicity or, for hematologic toxicities, any grade 3|4 that does not resolve to a grade 1|2 within 7 days per NCI CTCAE v4.03 toxicity criteria and is considered at least possibly related to ibrutinib and/or brentuximab vedotin, or any other regimen-related cause of death.

**Sample Size:**

Assuming 1) the ibrutinib 560mg and brentuximab vedotin 1.8mg/kg doses are well tolerated and 2) the study does not close for futility, 39 evaluable (received at least one cycle of treatment) patients will be enrolled on the phase II portion of the study. Note: Expected accrual for safety lead-in segment: n=9.

Estimated Duration of the Study
In the event that the study does not close for futility, accrual is expected to be completed in 45 months; with approximately 1-2 patients enrolled each month. Patients will be treated in 21-day treatment cycles until disease relapse, progression, unacceptable toxicity, or withdrawal of consent. Patients who discontinue study treatment for reasons other than disease relapse/progression will continue to have disease assessments per Cheson criteria  until relapse or progression, initiation of new anticancer treatment, or death whichever occurs first. Patients will be followed to collect further anticancer treatment (including HCT) and survival information until death, loss to follow-up, withdrawal of consent, study termination or up to 24 months post completion/ discontinuation of treatment.
Summary of Subject Eligibility Criteria:
Inclusion Criteria:

 
1) Relapsed/refractory biopsy-proven CD30+ Hodgkin Lymphoma
 
2) Age <math>\geq</math> 15 years old and <math>> 40\text{kg}</math>
 
3) ECOG Performance status 0-2
 
4) Prior exposure to brentuximab vedotin (relapsed disease after 3 month, not refractory disease) is allowed
 
5) Prior autologous hematopoietic cell transplant is allowed
 
6) Prior allogeneic hematopoietic cell transplant (allo-HCT) is allowed, provided there is no active GVHD and the patient is not taking immunosuppressive agents. Patient has to be at least 3 months out of allo-HCT.
 
7) Prior radiation therapy is allowed.
 
8) Patients may be on steroids before initiation of treatment, provided that use was tapered down to <math>\leq 20</math> mg prednisone or equivalent by cycle 1 day 1.
 

Exclusion Criteria:

 
1) Patients may not have developed progressive disease with prior treatment with brentuximab vedotin and may not have hypersensitivity to the drug. Prior ibrutinib for HL is not allowed.
 
2) Age <math>< 15</math> years old or <math>\leq 40\text{kg}</math>
 
3) Patients may not be taking other investigational products or concurrent biological therapy, chemotherapy, or radiation therapy.
 
4) Platelet count <math>< 50,000</math>, ANC <math>< 1,000</math>, hemoglobin <math>< 8.5</math>. (Growth factor support or transfusions to achieve targets are allowed provided that they have not received growth factor support for at least 14 days prior to entering trial)
 
5) Patients should not have any uncontrolled illness or active infection, including detectable HIV, HCV, and HBV. Patients with recent infection requiring systemic treatment that was completed <math>\leq 14</math> days before the first dose of study drugs are ineligible.
 
6) Unresolved toxicities from prior anti-cancer therapy, defined as having not resolved to Common Terminology Criteria for Adverse Event (CTCAE, version 4.03) grade 0 or 1, or to the levels dictated in the inclusion/exclusion criteria with the exception of stable neuropathy, vitiligo, alopecia, or other irreversible toxicity not reasonably expected to be exacerbated by study treatment (e.g., hearing loss)
 
7) Patients must not be vaccinated with live, attenuated vaccines with 4 weeks of the first dose of the study drugs.
 
8) Patients with active CNS disease or history of brain metastases are ineligible.
 

- 9) Patients must not have another malignancy within 3 years of enrollment. Exceptions: complete resection of basal cell carcinoma or squamous cell carcinoma of the skin, an in situ malignancy, or low-risk prostate cancer after curative therapy.
- 10) Pregnant women are excluded from the study.
- 11) Patients with a myocardial infarction within 6 months, or those with severe or poorly controlled cardiovascular illness are ineligible.
- 12) Patients must not have baseline grade II peripheral neuropathy.
- 13) Patients must not have known bleeding disorders, or history of stroke or intracranial hemorrhage within 6 months before enrollment.
- 14) Concomitant use of warfarin or other vitamin K antagonists is not allowed. Patients requiring treatment with a strong cytochrome P450 (CYP) 3A4 inhibitor are ineligible. (see Appendix 1)
- 15) Unable to swallow capsules or malabsorption syndrome, disease or condition significantly affecting gastrointestinal function, or resection of the stomach or small bowel, or partial or complete bowel obstruction
- 16) Currently active, clinically significant hepatic impairment Child-Pugh class B or C according to the Child Pugh classification

#### **Investigational Product Dosage and Administration:**

- Ibrutinib 560mg orally daily (expected dose, phase II)
- Ibrutinib 420mg and 560mg orally daily (planned doses, safety lead-in)
- Brentuximab vedotin (commercial supply) 1.8mg/kg intravenously every 3 weeks
- 1 cycle = 21 days

#### **Clinical Observations and Tests to be Performed:**

Physical exams, tumor measurements by radiographic imaging, blood tests to examine toxicities, and analysis on lymphoma specimens. See section 9.0 for details.

#### **Statistical Considerations:**

The primary hypothesis is that, in patients with relapsed/refractory Hodgkin Lymphoma (HL), the two agent combination ibrutinib and brentuximab vedotin (BV) can increase the complete response (CR) rate.

In a multi-center phase II trial investigating the use of single agent BV in relapsed/refractory HL patients post-AHCT, the overall response rate was 75%, the CR rate was 34%. Although single agent BV therapy is associated with a high overall response rate and tolerable toxicity, the CR rate and the duration of response can be improved.

The primary objective is to evaluate the antitumor activity of the two agent combination ibrutinib and brentuximab vedotin, as assessed by complete response (CR) rate, in patients with relapsed/refractory HL. The primary endpoint is a confirmed tumor response of CR and is based on the Cheson Criteria. A single cycle of treatment will be given in a 21 day cycle. Each patient's disease status will be evaluated at baseline; response will be assessed as outlined in the study schema.

**Statistics/Sample Size and Accrual:** This study will implement a Simon Two-Stage (Minimax) Design to evaluate the activity of the two agent combination ibrutinib and brentuximab vedotin. The null hypothesis that the true CR rate is 30% will be tested against a one-sided alternative. The phase II portion of the study is expected to enroll a minimum of 19 and a maximum of 39 patients.

The sample size is based on the desire to discriminate a promising CR rate of 50% from a disappointing response rate of 30% using a type I error rate of 0.05 and power of 80%.

During the first stage, 19 patients will be entered on the study. If  $\leq 6$  complete responses are seen, the study will be terminated. If at least 7 patients achieve a complete response, the trial will continue to the second stage.

At the second stage, 20 additional patients will be entered. At the end of stage 2, if 17 or more patients experience a complete response, the combination will be considered worthy of further study. If  $\leq 16$  patients experience a complete response then no further investigation of the combination is warranted. A total of 39 patients will be included in the phase II portion of trial. The study will also have a lead in phase where a minimum of three patients will be enrolled with 420 mg oral daily dosing of ibrutinib.

**Analysis:** All patients who met the eligibility criteria (with the exception of those who received no study medication) will be included in the main analysis of response and survival endpoints and all of the secondary or correlative analysis described below.

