## 2.2 Overview of Proposed Study

This is an open label, multi-center phase II study of ibrutinib and brentuximab vedotin in patients with relapsed/refractory Hodgkin lymphoma. Ibrutinib will be given 560mg orally daily; brentuximab vedotin will be administered intravenously at 1.8mg/kg once on the first day of each cycle. Each cycle is 21 days. The primary efficacy endpoint of this study is complete response rate. Response will be assessed according to modified criteria for malignant lymphoma, based on (Cheson et al. 2014) and (Cheson et al. 2007). Response assessment will be performed after cycles 2, 4, 7, 10, 13, and 16. Patients who achieve complete response (CR) can stop treatment after they have received 2 cycles of therapy post CR and at least 4 cycles of treatment. For patients who develop progressive disease while off treatment, they can return to treatment again provided that they have not received other investigational agents during the period of the protocol. (Autologous stem cell transplantation or allogeneic stem cell transplantation are allowed).

This study will be conducted in compliance with the protocol, Good Clinical Practice (GCP), and the applicable regulatory requirements.

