### 11.1 Study Design

#### 11.1.1 Phase II

The primary hypothesis: in patients with relapsed/refractory Hodgkin Lymphoma (HL), the two agent regimen combination of ibrutinib and brentuximab vedotin (BV) can increase the complete response (CR) rate.

In a multi-center phase II trial investigating the use of single agent BV in relapsed/refractory HL patients post-AHCT, the overall response rate was 75%, the CR rate was 34%. Although single agent BV therapy is associated with a high overall response rate and tolerable toxicity, the CR rate and the duration of response can be improved.

This multi-center, single arm phase II trial will implement a Simon Two-Stage Minimax Design (Simon 1989; Jung 2004) to evaluate the antitumor activity of the two agent combination ibrutinib and brentuximab vedotin, as assessed by complete response (CR) rate, in patients with relapsed/refractory Hodgkin lymphoma. The study is expected to enroll a minimum of 19 and a maximum of 39 patients. The sample size is based on the desire to discriminate a promising CR rate of 50% from a disappointing response rate of 30% using a type I error rate of 0.05 and power of 80%.

At stage 1, 19 patients will be entered on the study. If  $\leq 6$  complete responses are seen, the study will be terminated. If at least 7 patients achieve a complete response, the trial will continue to the second stage.

At stage 2, 20 additional patients will be entered. At the end of stage 2, if 17 or more patients experience a complete response, the combination will be considered worthy of further study. If  $\leq 16$  patients experience a complete response then no further investigation of the combination is warranted.

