### 11.4 Statistical Analysis Plan

In general, data will be summarized by using counts and percents for discrete parameters, and by descriptive statistics (number of observations, mean, standard deviation, median, minimum and maximum) for continuous parameters. The complete response rate will be calculated as the percent of evaluable patients that have confirmed CR; exact 95% confidence intervals will be calculated for this estimate. Observed toxicities will be summarized in terms of type (organ affected or laboratory determination), severity, time of onset, duration, probable association with the study regimen and reversibility or outcome. Baseline information (e.g. the extent of prior therapy) and demographic information will be presented as well to describe the patients treated in this study. Time to response and survival endpoints will be estimated using the product-limit method of Kaplan and Meier. The cumulative incidence of relapse/progression and non-relapse mortality will be calculated as competing risks.

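### Does 'confirmed' CR in the analysis text, against plain CR in the stage rules, leave the primary count open?

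*Combined protocol and SAP*

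**What the plan says.** Two places attach the word 'confirmed' to the primary endpoint. The Synopsis, Statistical Considerations, has "The primary endpoint is a confirmed tumor response of CR". Section 11.4 has "The complete response rate will be calculated as the percent of evaluable patients that have confirmed CR".

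Elsewhere the word is absent. The Synopsis Endpoints entry reads "The primary study endpoint is complete response (CR) rate". The stage 1 rule in the Synopsis Study Design is "If at least 7 patients achieve a complete response, the trial will continue to the second stage", and the final rule in section 11.1.1 is "if 17 or more patients experience a complete response, the combination will be considered worthy of further study".

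On timing, the Synopsis says that "response will be assessed as outlined in the study schema". The schema is a figure that is not in the text available for review. Section 2.2 says "Response assessment will be performed after cycles 2, 4, 7, 10, 13, and 16", and that patients in CR "can stop treatment after they have received 2 cycles of therapy post CR and at least 4 cycles of treatment".

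**The concern.** In an open-label, single-arm trial with investigator-assessed response, the definition of a counted response should be fixed before results are known. Two things appear to be open.

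The first is the word itself. If 'confirmed' means a second scan, some responders could be lost. Under section 2.2, a patient first in CR after cycle 4 may stop after cycle 6, one cycle before the assessment after cycle 7. The same one-cycle gap follows a first CR at cycle 7, 10 or 13. A patient who goes to transplant in that gap would have no second scheduled scan and could be counted as a failure, although transplant is a planned route for responders. A first CR at cycle 2 is not exposed, because the cycle 4 assessment still follows. Nor are patients who stop without transplant, because they stay under disease assessment.

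The second is the counting window. Sections 3.0 and 5.2 allow retreatment and re-entry after transplant. No sentence says that a partial responder who first reaches CR on such a later course is excluded from the primary count. Counting such patients would push the false-positive rate above its design value.

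**Working it through.** **1. The design as stated.** Inputs from section 11.1.1: null rate 30%, target rate 50%, 19 patients in stage 1, 20 more in stage 2, continue with at least 7 CRs, succeed with at least 17 of 39. The probability of success at a true counted rate p is

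P(p) = Σ over x = 7 to 19 of Bin(x; 19, p) × Pr(Y ≥ 17 − x), with Y ~ Bin(20, p).

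- P(0.30) = 0.0455, within the stated 0.05.
- P(0.50) = 0.8036, which meets the stated 80%.
- The probability of stopping at stage 1 is 0.6655 at 30% and 0.0835 at 50%. The expected sample size at 30% is 19 + 20 × (1 − 0.6655) = 25.7.
- A full search for the smallest total size that meets both error limits returns 39, and the 6/19, 16/39 rule has the smallest expected size under the null among designs of that size.

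The design arithmetic is right. The only question is which CRs enter x and Y.

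**2. What 'confirmed' can mean.**

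- Section 10.3 has the response category decided at every assessment. Its one added condition for CR is a negative follow-up marrow when the baseline marrow was positive.
- Section 10.1 starts the duration of CR when the criteria are first satisfied, not at a second scan.
- Section 10.3 does not require another PET-CT after a negative one, which fits poorly with a repeat-PET rule.
- Note b of the study calendar does mention two CT documentations of CR, but only to lengthen the scan interval.
- The Synopsis Statistical Considerations gives the confirmed endpoint and, a few lines later, the 7-of-19 and 17-of-39 rules. The natural reading is that 'complete response' in the rules is shorthand for the endpoint just named.

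Read together, 'confirmed' means established under the response criteria. The counts in section 11.4 and in the stage rules are then the same, and step 1 stands unchanged.

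**3. Size under the less likely repeat-scan reading.** Suppose the 30% and 50% rates refer to CR without a repeat scan, and a share u of CRs is never confirmed. The counted rate is then p(1 − u). The values of u are assumptions; the documents give none.

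| u | Expected CRs lost, 39 × 0.5 × u | Counted rate at 50% | Power | Counted rate at 30% | Type I error |
|---|---|---|---|---|---|
| 0 | 0 | 0.500 | 0.804 | 0.300 | 0.0455 |
| 2% | 0.39 | 0.490 | 0.769 | 0.294 | 0.0380 |
| 5% | 0.98 | 0.475 | 0.710 | 0.285 | 0.0286 |
| 10% | 1.95 | 0.450 | 0.599 | 0.270 | 0.0170 |

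This reading costs power but cannot produce a false claim of activity.

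**4. The counting window.**

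- The Synopsis entry on study duration ends off-treatment disease assessment at relapse, progression, new anticancer treatment or death. Its next sentence, on later follow-up, lists HCT among further anticancer treatments. Transplant therefore closes response assessment.
- The secondary objectives treat post-transplant outcomes as a separate question. Section 10.2 gives them their own endpoints, timed from HCT: survival, progression-free survival, relapse, non-relapse mortality, mobilization and engraftment. CR is not among them.
- The post-transplant disease form in Table 12.3.1 serves those relapse and progression endpoints.
- Section 5.2 opens retreatment to responders who have since relapsed, which is also where the first-course assessment has ended. Under section 3.0, patients who return after transplant are screened again.

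Nothing here credits a later CR to the first course, and several provisions point the other way.

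**The case for a change.** The strongest reply is that the margin is thin. Exact power is 80.4% against a target of 80%, and a result of 16 or 17 CRs turns on one patient. At an assumed 5% of CRs unconfirmed, about one of 19.5 expected CRs is lost and power falls by roughly nine points. The follow-up rule in the Synopsis governs when scans stop; it is not itself an endpoint definition. Settling the wording would need no extra patients.

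Part of this stands. 'Confirmed' is undefined in the text available for review, and the first-course limit has to be read from several sections. If the sponsor did intend a repeat scan, the power figures above show the kind of loss involved.

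It does not make the case for a change. The shares are hypothetical, and the reading that fits sections 10.1 and 10.3 has no loss at all. The obvious edits also have drawbacks. Deleting the word would relax the endpoint if a repeat assessment was meant. Adding a confirmed-CR sensitivity analysis would rely on the same undefined term, and it would lack a second scan for the very patients who go to transplant. Finally, the plan refers response timing to the schema, so its absence from the extracted text cannot be held against the plan.

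**Conclusion.** The concern does not hold as a defect that needs a change. The wording is uneven, but the response sections, the follow-up rule and the transplant endpoints lead an analyst to one count: CR by the response criteria in the first treatment course, before transplant, other anticancer therapy or retreatment. On that count the rules of 7 of 19 and 17 of 39 keep their exact type I error of 0.0455 and power of 0.804.

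This rests on reading 'confirmed' as documented by the criteria, and on the unseen schema not saying otherwise. If a repeat scan were required, power would be between 76.9% and 59.9% for assumed losses of 2% to 10% of CRs, with type I error below the design value. The documents support no estimate of how many later-course CRs could be miscounted, so no figure is given for that route.
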